1.3 SCHEDULE OF ACTIVITIES

	Eligibility screening (Pre-consent)	Baseline Day 1	3-Mo Follow-up Day 90 -14/+30	6-Mo Follow-up Day 180 -14/+30
Probable OUD diagnosis (NIDA myTAPS ¹ or past 90 day receipt of MOUD)	X			
Patient health questionnaire (PHQ-9) for depression ²	X			
Probable PTSD (PC-PTSD-5) ³	X			
Age 18 or older	X			
Patient at participating clinic	X			
Current receipt of both MOUD and psychotropic medication from provider(s) outside of the participating primary care health system (exclusion criterion)	X			
Speak English or Spanish	X			
Informed consent	X			
Randomization		X		
Adverse event reporting		X	X	X
Outcome Evaluation				
MOUD continuity of care ⁴ (max number of continuous (i.e., no breaks of more than 7 days) days on MOUD; EHR review)			X	X
MOUD access (receipt of MOUD prescription within 30 days of diagnosis; EHR review) ⁵		X	X	X
MDD symptoms (PHQ-9 ² raw score change)		X	X	X
PTSD symptoms (PCL-5 raw score change)		X	X	X
Drug use frequency (NSDUH ⁶ items)		X	X	X
Opioid use severity (PROMIS Substance Use Short Form ⁷)		X	X	X
Alcohol use (AUDIT-C ⁸)*			X	X
Opioid overdose risk behaviors (Opioid Overdose Risk Assessment ⁹)		X	X	X
Opioid overdose events (Naloxone Overdose Baseline Questionnaire ¹⁰)		X	X	X
MDD remission (PHQ-9 ² score < 10)		X	X	X
MDD response (PHQ-9 ² score < 50% of baseline)		X	X	X
PTSD remission (PCL-5 score < 34)		X	X	X
PTSD response (PCL-5 score < 50% of baseline)		X	X	X
Suicidality (Columbia Suicide Severity Rating Scales ¹¹)		X	X	X
All-cause mortality (death records)			X	X
MOUD initiation ¹² (receipt of MOUD prescription within 14 days of diagnosis; EHR review)			X	X
MOUD engagement ¹² (receipt of two or more MOUD prescriptions within 34 days of diagnosis; EHR review)			X	X
Access to MDD and/or PTSD treatment (receipt of medication and/or behavioral treatment associated with diagnosis; EHR review)			X	X
Quality of care for MDD ¹³ (4 psychotherapy visits in the first 8 weeks or an adequate (12-week) medication trial)			X	X
Quality of care for PTSD ¹³ (4 psychotherapy visits in the first 8 weeks or an adequate (60-day) medication trial)			X	X

	Eligibility screening (Pre-consent)	Baseline Day 1	3-Mo Follow-up Day 90 -14/+30	6-Mo Follow-up Day 180 -14/+30
Veterans RAND 12-item General health functioning (VR-12 ¹⁴)		X	X	X
Demographics (sex, race, ethnicity, education level, marital status)		X		
Alcohol use severity (AUDIT ⁸)		X		
Pain levels (PEG Pain Monitor ¹⁵)		X	X	X

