Opioid use frequency	All study participants	Days of opioid use in the past 30 days from NSDUH	Total days of opioids use (0-30)	Survey
Opioid overdose events	All study participants	Opioid overdose events in the previous three months	Binary, at least 1 event	Survey
Overall Health				
Physical health functioning	All study participants	Veterans RAND 12-item Health Survey (VR-12) – physical health subscale	MEPS ¹ standard	Survey
Mental health functioning	All study participants	Veterans RAND 12-item Health Survey (VR-12) – mental health subscale	MEPS standard	Survey

^b Study participants means all study participants who consented and were randomized to the intervention or to EUC.

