3.4.2 Overview and General Principles

The primary analyses will be performed for the intention-to-treat population, which consists of all randomized subjects. All individual statistical hypotheses will be tested using two-sided tests, with adjustment for multiple testing using a Bonferroni or Benjamini-Hochberg correction. Primary outcomes will be analyzed at a Type I error rate of 1.25% to control the family-wise error rate at 5% (e.g., so $0.05/4=0.0125$ when using a Bonferroni correction or the first p-value threshold for significance with Benjamini-Hochberg). Similarly, secondary and exploratory outcomes will be analyzed at Type I error rates to control family-wise error rate at 5% within domain. See Table 2 and 3 for definition of secondary outcome domains and our exploratory outcomes.

Outcomes derived from the follow-up surveys are subject to nonresponse, and statistical hypotheses based on these outcomes will be tested using nonresponse weighted models, if necessary. Traditionally, a logistic regression model can be specified predicting response using the demographic characteristics listed in Table , the baseline characteristics listed in Table , and the randomized treatment assignment. The model is given by:

$$\log \left(\frac{\Pr(R_{ij}=1)}{1-\Pr(R_{ij}=1)} \right) = \eta_j + \mathbf{X}_{ij} \boldsymbol{\theta} + \gamma T_{ij} + \rho P_{ij}$$

where η_j represent health system fixed effects. The nonresponse weight for participant i in health system j is given by $w_{ij} = \frac{1}{p_{ij}}$, where $p_{ij} = \Pr(R_{ij} = 1)$. However, we will utilize a nonparametric machine learner to estimate our nonresponse weights to allow for more complex relationships between the predictors variables and the odds of being a responder, thereby producing more high-quality nonresponse weights if they are deemed necessary.

To assess whether there is a need for use of nonresponse weights in our final analyses, we will assess how representative our sample of responders is for each outcome using effect sizes (ES) differences. If most of the ES differences are small (e.g., less than 0.1 or 0.2), we will feel good about the representativeness of our sample of responders to the original baseline sample and not utilize nonresponse weights in our final analyses.

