3.5.2 Secondary outcomes

Secondary endpoints are grouped into domains of conceptually related endpoints, and the outcomes will be analyzed adjusting for multiple comparison within domain using a Bonferroni correction. Table 8 provides the grouping of the secondary outcomes into domains, along with the observed outcome distributions, the minimum detectable effect size at 80% power and a family-wise error rate of 5%, and a reference effect size (if available). The vast majority of secondary outcomes are sufficiently powered to detect clinically meaningful effects or effects found in similar interventions.

Table 9: Minimum detectable effect size for secondary outcomes

Outcome	Observed distributions	Minimum detectable effect size	Reference effect size
Mental Health			
Access to MDD and/or PTSD treatment	
 • N=259 • 65.5% access treatment 	19.2 percentage points	None
Quality of care for MDD	
 • N=210 • 8.8% with quality care 	18.9 percentage point	16 percentage points for medication adherence ¹² at 3 months
Quality of care for PTSD	
 • N=300 • 9% with quality care 	15.3 percentage point	Expect similar to MDD
MDD remission	
 • N=405 • 16.0% remission 	15.0 percentage points	15 percentage points ¹³
MDD response	
 • N=405 • 26.2% response 	15.8 percentage points	20 percentage points from CALM ¹³ or 23 percentage points from STEPS-UP ¹¹
PTSD remission	
 • N=368 • 56.2% remission 	17.8 percentage points	Similar to MDD remission
PTSD response	
 • N=365 • 21.6% response 	17.7 percentage points	18 percentage points ¹¹

Active suicidal ideation	
• N=523• 24.2% at 6-months	14.5 percentage point	Any reduction
--------------------------	---	-----------------------	---------------

Substance Use

Opioid use frequency	
• N=523• Mean (sd) = 4.3 (9.6)	0.27 standard deviations; 2.6 raw scale	None
----------------------	---	---	------

Opioid overdose events	
• N=525• 2.1% at 6-months	5.9 pct point reduction	None
------------------------	--	-------------------------	------

Overall Health

Physical health functioning	
• N=525• Mean (sd) = 36.8 (12.0)	3.2 points	Similar to mental health functioning

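### The overdose endpoint counts only survivors' reports at the 6-month survey, so 3-month reports and overdose deaths enter no efficacy analysis; the detectable reduction stated for it in SAP Table 9 is impossible

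*SAP*

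**What the plan says.** The Substance Use part of SAP Table 2 (section 2.5.2) lists "Opioid overdose events in the previous three months" for all study participants, scored as "Binary, at least 1 event", with the survey as the only source. The row names no survey wave.

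Other parts of the SAP point to the 6-month survey:
- Table 9 (section 3.5.2) gives N=525 and "2.1% at 6-months".
- Table 7 has columns for baseline and 6 months only.
- The response indicator in section 3.4.1 refers to the 6-month survey.
- Section 1.2 records that repeated-measures analyses were removed.

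The Protocol's Schedule of Activities (section 1.3) marks the overdose item at baseline, 3 months and 6 months. It also marks "All-cause mortality (death records") at both follow-ups, and Protocol 10.1.3 describes obtaining mortality from state vital records. SAP 1.2 records that the mortality analysis was dropped, and no mortality outcome appears in Tables 1 to 3. The SAP gives no rule for participants who die.

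On power, Table 9 states "5.9 pct point reduction". The text above the table describes such figures as "the minimum detectable effect size at 80% power and a family-wise error rate of 5" per cent, and says "the outcomes will be analyzed adjusting for multiple comparison within domain using a Bonferroni correction". Section 3.4.2 adds: "All individual statistical hypotheses will be tested using two-sided tests".

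**The concern.** Three things are at stake.

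**Early events.** A look-back of about three months from the 6-month interview does not reach the first part of follow-up. Care-coordinator contact is most frequent then: weekly for two months and biweekly in the third (Protocol 6.1.1). By contrast, buprenorphine continuity is counted over all 180 days.

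**Deaths.** A participant who dies of an overdose cannot answer the survey and becomes a non-responder. The optional nonresponse weights would let responders stand in for that person; they would not count the death as an event. An arm with more overdose deaths could therefore look no worse on this row. Lowering overdose and suicide risk is the stated purpose of CC-COD+, which is pooled into the intervention arm.

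**The power statement.** A reduction cannot exceed the rate it starts from. A reader of Table 9 would take the endpoint to be able to detect a benefit of a stated size when it cannot.

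**Working it through.** **Inputs.** N=525, event rate 2.1%, 80% power and 5% family-wise error (SAP 3.5.2). Two outcomes in the Substance Use domain, so Bonferroni alpha = 0.05/2 = 0.025, two-sided, z = 2.2414. Allocation 1:1 (SAP 2.7), so n = 525/2 = 262.5 per arm. Randomised total 797 (SAP 2.6).

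**Counts.** 0.021 × 525 = 11 people with an event. 525/797 = 65.9%, so 272 randomised participants (34.1%) have no value. Each uncounted overdose death would equal 1/11, about 9% of the counted events.

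**Formula.** Power = Φ[(d − 2.2414 × se0)/se1], with d = |p1 − p2|, se0 = √[p̄(1 − p̄) × 2/n] and se1 = √[(p1(1 − p1) + p2(1 − p2))/n].

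**Check of alpha.** For opioid use frequency in the same domain (N=523, SD 9.6), (2.2414 + 0.8416) × √(2/261.5) = 0.270 SD, or 2.59 days. Table 9 states 0.27 SD and 2.6, so alpha 0.025 is the level the SAP used.

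**Reproducing 5.9 points.**
- Increase from 2.1% to 8.0%: d = 0.059, se0 = 0.01911, se1 = 0.01894. Power = Φ[(0.059 − 0.04284)/0.01894] = Φ(0.853) = 80.3%. Solving for exactly 80% gives 5.87 points, so the figure reproduces as an increase.
- Decrease of 5.9 points from 2.1%: the second rate would be −3.8%, which is impossible.

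**What a reduction could achieve.**
- If 2.1% is the control-arm rate, elimination (2.1% to 0%) has d = 0.021, se0 = 0.00890, se1 = 0.00885. Power = Φ[(0.021 − 0.01994)/0.00885] = Φ(0.12), about 55%.
- If 2.1% is the rate over both arms, solving with p̄ = 0.021 gives d = 3.85 points, which is about 4.0% versus 0.2%.
- Halving from 2.1% to 1.05% has about 10% power.

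**Adding the 3-month survey.** The documents give no 3-month overdose rate, so the combined rate is an assumption. If the 3-month survey adds no new people, the rate stays at 2.1%. If it adds as many again with no repeat reporters, it is 22/525 = 4.2%. N is held at 525 and the combined rate is taken as the control-arm rate.

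| Combined rate | Power, elimination | Power, halving |
|---|---|---|
| 2.1% | 55% | 10% |
| 3.1% | 74% | 15% |
| 4.2% | 87% | 19% |

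At 4.2% the detectable reduction is 3.96 points, to about 0.24%: 3.96/4.2 = 94% of events removed.

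**Window coverage.** Interviews may fall 14 days early or 30 days late (Protocol 1.3). Taking three months as 90 days:
- The 6-month interview falls on days 166 to 210, so its look-back starts between day 76 and day 120.
- The 3-month interview falls on days 76 to 120, so its look-back starts between day −14 and day 30.
- A 3-month interview on day 76 followed by a 6-month interview on day 210 leaves days 76 to 120 uncovered, a gap of 44 days.

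**The case against.** The 6-month anchor is consistent across the SAP. The move away from repeated measures was made while answering data monitoring board queries, and measuring after the intervention has taken hold is defensible. Replacing a prespecified secondary endpoint after data collection, with its overall event rate already known, would be worse than leaving it. That stands, and is why the endpoint should be kept and supplemented.

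Four stronger readings are tempting, but the documents do not support them:

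- A reader might infer that the trial ignores fatal overdoses. It does not. Deaths, and non-lethal overdoses with an emergency visit, are reportable serious adverse events (Protocol 8.3.3.1) and go to the monitoring board. The gap is in the efficacy analyses.
- A reader might infer that overdose deaths are ready to be counted. The documents schedule all-cause mortality but specify no cause-of-death field, and the serious-event list has no category for overdose death.
- A reader might infer that no reduction at all can reach 80% power. That holds only if 2.1% is the control rate. Table 9 labels it an observed distribution and the calculations preceded unblinding, so it may well be the pooled rate; then 4.0% versus 0.2% would suffice.
- A reader might infer that using both surveys cures the shortage of events. Twenty-two events require a constant rate and no one reporting in both windows. Even then only near-elimination is detectable, and the two look-backs do not neatly cover days 0 to 180.

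**Conclusion.** The point holds on two counts.

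First, the overdose endpoint as planned leaves 3-month reports and overdose deaths out of every efficacy analysis. The 6-month wave is inferred from Tables 7 and 9 and section 3.4.1, because the Table 2 row does not state it. The effect on the treatment comparison cannot be sized: the documents give neither the 3-month rate nor the number or causes of deaths. With about 11 events counted, a handful of deaths unevenly split between arms could alter the picture.

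Second, the Table 9 row is wrong as written, whatever is decided about the definition. A 5.9-point reduction from 2.1% cannot occur; the figure is a detectable increase. The endpoint can show only near-total removal of overdoses, under either reading of the 2.1%.

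The gain from the fix is mainly validity, because early events and deaths would be counted. Power stays poor across the assumed 2.1% to 4.2% range.

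**What to change.** 1. **Table 9.** Correct the row: describe 5.9 points as an increase, or replace it with the reduction calculation. State whether 2.1% is the control or the pooled rate, and say that the endpoint is not powered for a plausible reduction.
2. **Table 2.** State the 6-month survey as the wave and keep this as the prespecified secondary endpoint.
3. **Supplementary analysis.** Add, labelled and dated relative to unblinding, any overdose reported at the 3- or 6-month survey, or overdose death where cause is available. Give rules for people who answered only one survey and for deaths of unknown cause. Report all deaths by arm.

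Items 1 and 2 cost only wording. Item 3 uses a survey item already scheduled at 3 months, but it also depends on whether mortality records were obtained and whether they show cause. The SAP revision that dropped the mortality analysis cites time and budget limits, so this may take further work. The analysis should also state its limits: some look-backs may reach before randomisation, others leave a gap of some weeks, and cause of death may not be available.

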2.5.3 Exploratory outcomes

There are five potential exploratory outcomes, which are described in Table 3.

Table 3: Definition of Exploratory Outcomes

Outcome	Population ^c	Definition	Measure Scale	Source
Drug use frequency	All study participants	Maximum days of use in the past 30 days for five drug categories using items from NSDUH (prescription opioids, heroin, cocaine/crack, methamphetamine/ other stimulants, and tranquilizers/sedatives)	Total days of use of most frequent drug (0-30)	Survey
Stimulant use frequency	All study participants	Days of stimulant use (cocaine/crack, methamphetamine/ other stimulants) in the past 30 days from NSDUH	Total days of stimulant use (0-30)	Survey
Alcohol use	All study participants	Alcohol Use Disorder Identification Test – Consumption (AUDIT-C) for the previous 3 months	Sum of items (0-12)	Survey
Opioid overdose risk behaviors	All study participants	Opioid Overdose Risk Assessment	Sum of items (0-32)	Survey
Opioid use severity	All study participants	Patient-Reported Outcomes Measurement Information System (PROMIS) Substance Use Short Form for the previous 30 days	Sum of items (7-35)	Survey

2.5.4 Other measures

Table 4 provides the definition of additional measures that will be used as potential mediators and moderators in exploratory analyses described below.

Table 4: Definition of additional potential mediation and moderation variables

Measure	Instrument	Measure Scale	Source
Potential Moderators			
Trauma/Interpersonal Violence	PTSD Checklist for DSM-5, description of worst event	Categorical*	Survey
Sex	Sex on current birth certificate	Categorical**	Survey
Ethnicity	Patient-reported ethnicity	Binary (Hispanic/non-Hispanic)	Survey
Pain	PEG Pain Monitor, for past week	Mean of 3 items (0-10)	Survey
Disability and impairment	Sheehan Disability Scale	Sum of 3 items (0-30)	Survey
Stimulant use frequency	Days of stimulant use (cocaine/crack, methamphetamine/ other stimulants) in the past 30 days from NSDUH	Total days of use (0-30)	Survey
Housing status	Homelessness Screening Clinical Reminder	Categorical***	Survey
Number of care coordinator visits	Care coordinator entry of visits with patient	Continuous	Registry
Potential Mediators			
Clinician communication	CAHPS ECHO	0-100	Survey
Ability to quickly access treatment	CAHPS ECHO	0-100	Survey
Overall rating of treatment	CAHPS ECHO	0-100	Survey
Patient and care coordinator working alliance	Working Alliance Inventory	Mean of 12 items (min=1, max=5)	Survey

*no trauma, trauma w/o IPV, trauma w/ IPV; **male, female, gender neutral; ***stably housed, unstably housed, unhoused

2.6 Study design

This study is a stratified randomized trial testing CC-COD versus EUC, with strata defined by prior MOUD exposure and primary care clinic.

As part of the CR, we initially planned to compare CC-COD+ to CC-COD, with MOUD continuity of care as the primary outcome. However, despite sustained and targeted efforts, recruitment was lower than expected, and we did not reach our targeted enrollment goals for either CC-COD or CC-COD+. Based on input from our research advisory board and NIH project officer, we now plan to combine the CC-COD and CC-COD+ samples when analyzing the data for additional information about the potential effectiveness of the intervention. Since the Collaborative Care Model is identical across both trials, and the only difference between the arms is in the additional clinical modules supported by CC-COD+, combining the active CC-COD and CC-COD+ arms for an exploratory analysis should provide additional precision around the estimated treatment effect for CC-COD/CC-COD+.

The study's original target sample size was 900, with an additional 300 patients targeted for the CR, for a combined target of 1200. Our final sample size was 797 (729 following the original protocol and 68 following the protocol from the CR). This analysis plan has been modified to include actual final power calculations calculated prior to breaking the blind but after all data collection ended.

2.7 Randomization

After a baseline assessment, study participants will be randomized 1:1 into CC-COD/CC-COD+ or EUC. A stratified randomization design will be used, with the strata determined by primary care clinic and prior MOUD exposure. A randomization list will be generated for each stratum and include randomly permuted block sizes of 2 and 4. We will stratify on prior MOUD to mitigate confounding, as patients who have used MOUD previously are more likely to initiate MOUD subsequently. Research staff will access the randomization module in REDCap. Staff will enter which prior MOUD exposure stratum and clinic the patient is in, and the intervention arm assignment will be generated.

We extended the randomized trial from the original study to implement CC-COD+. All participating clinics started the study with enrolled patients being randomized between CC-COD and EUC. Three health systems then transitioned to randomizing patients between CC-COD+ and EUC. The remaining health system did not transition to CC-COD+ because they did not enroll sufficient patients to justify transitioning to CC-COD+. Table 5 provides a timeline of when health systems transitioned to CC-COD+.

Table 5: Competitive Revision Recruitment Timeline

Site Groups	Date of CC-COD+ Transition
Health System 1 (includes 7 clinics)	08/29/2022
Health System 3 (includes 3 clinics)	07/13/2023
Health System 4 (includes 3 clinics)	08/28/2023

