8 STUDY ASSESSMENTS AND PROCEDURES

8.1 ENDPOINT AND OTHER NON-SAFETY ASSESSMENTS

Assessment Procedures. Once a potential participant has indicated interest in the study, trained research staff will screen the individual for eligibility. In the screening assessment, a research assistant (employed by the RAND/UNM research team) will ask the individual's age and whether they are receiving primary care at one of the eleven participating clinics. The research assistant (employed by the RAND/UNM research team) will then administer the NIDA Tobacco, Alcohol, Prescription medication and other Substance use (myTAPS) screener to assess for probable OUD, the 9-item Patient Health Questionnaire (PHQ-9) to assess for probable depression, and the Primary Care PTSD Screen for DSM-5 (PC-PTSD-5) to assess for probable PTSD.

Patients will be eligible to participate in the study if they meet the following criteria: age 18 or older; are receiving primary care at a participating clinic; probable OUD diagnosis, defined by myTAPS¹ scores ≥ 1 or past 90 day receipt of MOUD; have probable depression (a score ≥ 10 on the PHQ-9²) or probable co-occurring PTSD (having a score ≥ 3 on the PC-PTSD-5³); speak and understand English or Spanish; have capacity to give informed consent; and provide a signed and dated informed consent form. The screening process will be terminated if the patient indicates they do not meet any of the previous criteria. The only other reasons for exclusion from the study are if the patient requires immediate medical (emergency procedure needed) or psychiatric intervention (i.e., self-injured, active psychosis) or if the patient is receiving both MOUD and psychotropic medication from a provider outside of the primary care system at which the patient is enrolled.

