3.4.4 Continuous outcomes

Continuous outcomes will be analyzed using a linear regression model including health system, prior MOUD exposure, and treatment assignment as predictors. The linear regression model is given by:

$$y_{ij} = \alpha_j + \nu P_{ij} + \beta T_{ij} + e_{ij}$$

where α_j are clinic-level fixed effects, β is the effect of CC-COD over EUC, and e_{ij} is an independent and identically distributed mean zero error term. The statistical hypotheses from the linear regressions will be of the form:

$$H_0: \beta = 0 \text{ vs}$$

$$H_1: \beta \neq 0.$$

If necessary, outcomes that require elements from the 6-month follow-up survey may be weighted to account for nonresponse as previously described. Again, if we do not have sufficient sample size to support modeling P_{ij} (prior MOUD treatment), then it will be removed from a given model. We will assess this for each continuous outcome by examining if we have at least 30 individuals with and without prior MOUD treatment in our analytic sample.

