3.5 Statistical power

All calculations are for 80% power at a Type I error rate of 1.25%, which accounts for the multiple primary outcomes using a Bonferroni correction to control the family-wise error rate at 5% ($0.05/4 = 0.0125$). Actual calculations use the observed loss to follow up rate in the final sample.

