3.5.1 Primary outcomes

We used the observed distributions for our continuous variables including the following: for the planned power calculations were:

1. We observed a mean number of days until accessing Buprenorphine of 26.0 with a standard deviation of 31.9. Our total sample size for this analysis was 137 individuals with 6-month follow-up data.
2. Among those who initiate medication for OUD, the mean number of days of continuous treatment for OUD is 133.0 with a standard deviation is 54.1. The total sample size for this analysis was 392 individuals with 6-month follow-up data.
3. Among those with probable depression at enrollment ($\text{PHQ-8} \geq 10$), the mean depression symptoms score (PHQ-8) at 6 months of 11.5 with a standard deviation of 6.6. The total sample size for this analysis was 405 individuals with 6-month follow-up data.
4. Among those with probable PTSD at enrollment ($\text{PC-PTSD-5} \geq 3$), the mean PTSD symptoms score (PCL-5) at 6 months of 32.2 with a standard deviation of 17.8. The total sample size for this analysis was 368 individuals with 6-month follow-up data.

Under these observed outcome distributions as well as the final number of individuals with observed outcome values in our data, we have 80% power to detect:

1. A hazard ratio of at least 0.45 if we find a protective effect and see fewer days until accessing Buprenorphine. This corresponds to at least a hazard ratio of 2.25 if the direction were reversed or a 27-percentage point difference if the outcome was modeled as a binary measure. Notably, a previous study of Collaborative Care for opioid and alcohol use disorders found a 22-percentage point increase over enhanced usual care so if the effect is large in CLARO, we may be able to detect it.⁸
2. 18.3 additional days of continuous OUD treatment within the first 180 days. A growing body of evidence suggests the mortality is lower during OUD treatment, and that mortality is increased in the first four weeks after treatment cessation.⁹
3. A 2.2 point reduction in depression symptoms (PHQ-8). This provides power to detect effects below the clinically important difference for individual change of 5 points.¹⁰
4. A 6.23 point reduction in PTSD symptoms (PCL-5). A previous study of delivering PTSD treatment in primary care setting to active duty military found a reduction in PTSD symptoms of 7 points.¹¹

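### The primary buprenorphine-days model adjusts only coarsely for buprenorphine status at enrolment, through a prior-MOUD indicator with no stated drug, window or current-versus-past coding

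*SAP*

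**What the plan says.** **Who enters.** Protocol 8.1 accepts "past 90 day receipt of MOUD" as one way to meet the probable-OUD criterion. Protocol 5.4 lets clinic staff refer patients with OUD whether or not they are on buprenorphine or naltrexone. Treated and untreated patients are therefore randomized together.

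**How MOUD is used in the design.** Strata are clinic and prior MOUD exposure. SAP 2.7 gives the reason: "We will stratify on prior MOUD to mitigate confounding, as patients who have used MOUD previously are more likely to initiate MOUD subsequently".

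**How it is used in the analysis.** SAP 3.4.4 states: "Continuous outcomes will be analyzed using a linear regression model including health system, prior MOUD exposure, and treatment assignment as predictors". SAP Table 8 describes the MOUD term only as an indicator of prior treatment. Under SAP 3.4.4 the term is dropped if fewer than 30 people fall on either side of it. The wider set of baseline characteristics enters the nonresponse and mediation models, not this one.

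**The endpoint.** SAP Table 1 defines continuity as cumulative buprenorphine days in the 180 days after enrolment. It excludes participants on methadone at baseline but keeps those on buprenorphine. Protocol 9.3 lists all randomized participants for the same outcome.

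**The concern.** A patient filling buprenorphine at enrolment can begin accumulating days at once. A patient who stopped long ago must first restart. Under a lifetime reading of prior exposure, both carry the same value of the indicator. The rationale in SAP 2.7 is about who will start MOUD, which does not describe someone already on it.

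The methadone exclusion shows that the SAP already treats drug-specific status at baseline as knowable and relevant to this endpoint. Buprenorphine status gets no equivalent handling.

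Two things are at stake for a primary outcome tested at 1.25%. Variance that a baseline variable could explain stays in the error term. And if one arm happens to receive more current users, the model can correct for that only as far as the prior-MOUD indicator tracks current use.

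**Working it through.** **Inputs**

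- Power and error rate, SAP 3.5: "All calculations are for 80% power at a Type I error rate of 1.25%, which accounts for the multiple primary outcomes".
- Sidedness, SAP 3.4.2: "All individual statistical hypotheses will be tested using two-sided tests".
- Allocation, SAP 2.7: "study participants will be randomized 1:1 into CC-COD/CC-COD+ or EUC".
- Outcome distribution among those who initiate, SAP 3.5.1: "the mean number of days of continuous treatment for OUD is 133.0 with a standard deviation is 54.1", with N = 392 and a stated detectable effect of 18.3 days.
- Variance explained by enrolment buprenorphine status: not in the documents, so assumed and shown as a range.

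**Step 1. Reproduce the SAP figure.**
MDE = (z for 1 − 0.0125/2 + z for 0.80) × SD × √(4/N) = 3.339 × 54.1 × √(4/392) = 18.25 days. Power at 18.3 days with 196 per arm is 0.803. The stated 18.3 is reproduced, and it credits no variance reduction from any covariate.

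**Step 2. Add a covariate with assumed partial R².**
Residual SD = 54.1 × √(1 − R²), with everything else unchanged.

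| Assumed R² | Residual SD | MDE (days) | Power at 18.3 days |
|---|---|---|---|
| 0.05 | 52.7 | 17.8 | 0.83 |
| 0.10 | 51.3 | 17.3 | 0.85 |
| 0.20 | 48.4 | 16.3 | 0.89 |
| 0.30 | 45.3 | 15.3 | 0.93 |
| 0.40 | 41.9 | 14.1 | 0.97 |

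**Step 3. What that range means in days.**
If a share p are users at enrolment and their mean exceeds that of the others by g days, R² = p(1 − p)g²/54.1². With p = 0.5 (assumed), R² = 0.05 needs g = 54.1 × √(0.05/0.25) = 24 days, and R² = 0.40 needs g = 54.1 × √(0.40/0.25) = 68 days. These are gaps beyond whatever health system and prior MOUD already explain.

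**Step 4. Chance imbalance.**
For an unstratified factor at 50%, the SE of the between-arm difference in share is √(0.25 × 4/392) = 0.0505, so the 95% range is about ±9.9 percentage points. Multiplied by a gap of 40 or 60 days, this moves the unadjusted difference by up to about 4.0 or 5.9 days. These are upper bounds, because stratifying on and adjusting for prior MOUD removes part of the imbalance.

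**Step 5. Limit of the SD.**
The 54.1 describes initiators only, whereas the endpoint population includes people with zero days. If a share q initiate, the mean is 133q and the variance is q(54.1² + 133²) − (133q)². For q from 0.5 to 0.9 (assumed) the SD is about 65 to 78 days. With N = 392/q, the MDE is about 18.3 to 21.7 days. The table in Step 2 therefore shows the scale of the gain; it does not forecast it for the full set.

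**The case against.** The strongest reply is that nothing here is an error. The model adjusts for prior MOUD and for clinic collapsed to health system, which gives a valid test. Chance imbalance is already reflected in its standard error. If the stratum was coded from the 90-day screen, recent receipt is already in the model. Under a lifetime definition, current users would still normally be coded as exposed. Either way there is some adjustment, and the size of the gain rests on an assumed R². **All of this stands.** It makes the point one of efficiency and definition. It does not remove the gap, because under either coding the indicator pools buprenorphine with other MOUD and current with lapsed use.

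Three stronger readings are tempting, and the documents do not support them.

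- *Current status is wholly unadjusted, or the estimate is biased.* Neither follows, for the reasons just given.
- *The endpoint is dominated by people already on buprenorphine.* A reader might set the access count in SAP 3.5.1 ("Our total sample size for this analysis was 137 individuals with 6-month follow-up data") against the 525 followed participants in SAP Table 9, giving 26%, and take the rest as current users. But not being a new episode means recent OUD care, not a buprenorphine supply. The 525 is also the count for survey outcomes defined in all participants, whereas the SAP continuity set excludes baseline methadone users. The ratio does not estimate the share on buprenorphine.
- *The covariate is already derived, as the complement of the access-set rule.* Protocol 9.3 defines that rule by OUD-diagnosis visits in the past 30 days, and SAP Table 1 by no care. A patient can have a visit without buprenorphine, or a supply without a visit.

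**Conclusion.** The concern holds as a matter of precision and definition. The buprenorphine-days model in SAP 3.4.4 handles enrolment buprenorphine status only through an undefined prior-MOUD indicator. The planned test remains valid.

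The benefit of a direct covariate is unknown from the documents. Under the assumed partial R² of 0.05 to 0.40 it is worth roughly 0.5 to 4 days of detectable effect (18.3 down to 17.8 or 14.1), with the initiator-only SD and N = 392. If prior MOUD already tracks current use closely, the gain sits at or below the low end. That enrolment status predicts later days strongly is a reasonable inference, but the documents do not state it.

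The point is confined to continuity. The access endpoint is limited to new care episodes and so deals with recent care by restriction.

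**What to change.** In SAP 3.4.4, for buprenorphine continuity only:

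1. Add one prespecified covariate: an indicator of buprenorphine receipt at enrolment or in the 30 days before it. Derive it from the baseline MOUD-history items (Protocol 1.3), or from PMP fills where the pre-enrolment look-back is available. The documents do not state that look-back, so the source must be named.
2. Keep prior MOUD exposure in the model as the stratification term.
3. In SAP 2.7 and Table 8, state how prior MOUD exposure was coded at randomization: which drugs, what window, and whether current use counts.

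SAP 2.2 says the plan was finalized before unblinding. If the blind has since been broken, leave the primary model as it is and report the adjusted model as a labelled sensitivity analysis.

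The cost is one degree of freedom, a few lines of SAP text and a small derivation. The sources named are ones the trial already collects or obtains.
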